Clinical Study Protocol

Study Title: Impact of Providing Medical Records in a Patient-Centered, Community Pharmacy Based, HIV Care Model (HIV-MOI) of the Community Pharmacy-Based HIV Care Model study

ClinicalTrials.gov Identifier: NCT03437694

Sponsor: National Institute on Minority Health and Health Disparities

Sponsor Project Title: Texas Center for Minority Health, Education, Research and Outreach

FAIN Number: U54MD006882

IRB Number: 1436643/2018-094

Protocol Version/Date: Original Approval: 5/24/2019
Most Recent Approval: 10/17/2023

North Texas Regional Institutional Review Board (NTRIRB)

University of North Texas Health Science Center

PROTOCOL INFORMATION

Title of Research Activity: Medical record based versus non-medical record based community pharmacy provided medication therapy management

Name of Principal Investigator: [name], PharmD, BCIDP, BCPS (formerly known as [name])

Institution: UNTHSC

Sponsoring Agency / Company (if applicable): NIMHD

Sponsor's Protocol Number (if applicable): ClinicalTrials.gov Identifier: NCT03437694

Specific Aims –

- A. To investigate the change in control of diabetes and/or hypertension in adult African-Americans with HIV, who receive medication therapy management (MTM) from their community pharmacist when the pharmacist is provided the information from the participants' medical records (intervention) or not provided the information from the medical records (control, standard of care is no medical record information is provided). Control will primarily be determined using HgbA1c & plasma glucose from medical records (diabetes), and systolic blood pressure from medical records (hypertension) and these will be compared against nationally accepted standards for each condition. Control of HIV will be monitored (no change anticipated) via medical record provided HIV-RNA viral loads and CD4 counts.

Protocol version 9 October 2023

Medical record vs. Non-medical record

community pharmacy based MTM study

Page 1 of 31

B. Background and Significance

[figure not shown]

Figure 1: Adapted from Ribaudo 2016

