2) **Data Analysis and Data Monitoring** – Describe plans for statistical analysis of data when appropriate. If a data safety monitoring committee is appropriate to protect the safety and/or welfare of subjects, describe its operation (e.g., membership, stopping rules and frequency of review).

The diseases being used to validate HIV-CMTM effectiveness are HIV, DM and HTN. For HIV, disease control is defined as plasma HIV-RNA of < 20 copies/mL. Standard of care recommends follow-up based on viral load. (19) For DM, self-monitoring of blood glucose is less reliable than quarterly A1c levels (goal of \leq 7%) which is monitored every 3 months. In HTN, goals vary based on comorbid conditions as follow-up varies with medications. As AA have 2-3 higher incidental rates of stroke compared to whites. (Howard). As a 10 mmHg difference in systolic blood pressure is shown to reduce stroke rate by 24% in AA, a decrease in systolic blood pressure reductions of 10 mmHG [or attainment of blood pressure goal] was selected as the primary measure for effectiveness on HTN. Medical record blood pressure will be the primary source for analyses as ultimately, it is the information collected by the diagnostician that is used for decisions.

Two sample t-test for continuous outcomes (viral loads) and chi-square for categorical outcomes (blood pressure under control or not) would be used to assess significance at the 0.05 level.

DATA AND SAFETY MONITORING PLAN

There are no medical procedures or prescription changes that can occur as part of this study that are not first authorized by the patient's medical provider. A data safety monitoring plan has been presented and approved by the NIMHD Program and Science Officer that reflects the low safety risk to participants, from a medical perspective. The **DATA SAFETY PLAN** is attached. The risks to participants due to protection of information and how information is safely maintained is addressed elsewhere in the protocol.

3) **Data Storage and Confidentiality**

Data Security, Collection, Entry, Management, and Quality Control: Only authorized study personnel will have access to the data. All HIPAA research safeguards and protocols for protected health information will be observed. All randomized participants will be assigned a unique identification (UID) number for use throughout the project. This number will be

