Two hundred adult AA with HIV and either/both DM or HTN will be recruited using NTRIRB approved recruitment materials. Once consented, patient gender and comorbidity stratified randomization (i.e., separate randomization by men/women and by DM/HTN) will be used to randomize them into the intervention group or control. Randomization assignment will be controlled by the biostatistician. This will create eight groups: men with DM receiving intervention (1.a.), men with DM receiving control (2.a.), women with DM receiving intervention (1.b.), etc. (Figure 4). Patients with dual diagnosis of DM and HTN will be randomized into either the intervention or control group. Their data will be used in both DM and HTN analyses (after conducting a sensitivity analysis to determine that the dual diagnosis does not confound or bias the results). A random number generator (range 1 to 10,000) will be used for group assignment. UNTHSC biostatistician will be the only unblinded member of the research team to which number corresponds to the intervention or control groups when presenting data during investigator team safety reviews and data safety monitoring plan described.

The primary endpoint for this study will be the health indicators collected at the final follow-up visit comparing the corresponding intervention and control groups (e.g., intervention vs. control for men with diabetes). We computed the power and sample size based on the effect sizes estimated from our previous CDC-funded demonstration project where observations from 201 African American HIV patients at baseline whose viral loads were either detectable (>20 copies/mL) or their CD4 counts were <200 cells/mcL at baseline. Of these, 171 (85%) showed improvement (viral loads became undetectable or CD4 counts became >200 cell/mcL) at follow-up after receiving quarterly HIV-CMTM. Based on these results and even assuming a very conservative effect of 45% improvement for the control group receiving standard of care projects that a comparison between intervention and control will require 22 subjects per group. This enrollment volume enables attaining a power of at least 80% at the 0.05 level of significance for each of the comparisons. As some attrition is expected, we will recruit 25 patients per group for a total of 200 patients. We also note that the sample sizes are very likely larger as the subjects with a dual diagnosis of diabetes and hypertension will be included in the analyses, but are not included in the

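### Viral load is assigned a two-sample t-test with no stated scale and no rule for results below 20 copies/mL, although the plan defines HIV control as being below 20

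*Combined protocol and SAP*

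**What the plan says.** Section E.2 (Data Analysis and Data Monitoring) lists HIV with diabetes and hypertension as the diseases used to judge whether the service works. It sets the HIV criterion as a threshold: "For HIV, disease control is defined as plasma HIV-RNA of < 20 copies/mL". The analysis is then given in one sentence. It names "Two sample t-test for continuous outcomes (viral loads" and, for the other type of outcome, "chi-square for categorical outcomes (blood pressure under control or not"; these "would be used to assess significance at the 0.05 level". Viral load is the only example of a continuous outcome and blood pressure the only example of a categorical one.

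Specific Aim A gives HIV a lesser role: "Control of HIV will be monitored (no change anticipated) via medical record provided HIV-RNA viral loads and CD4 counts". Control is to be judged primarily on HbA1c, plasma glucose and systolic pressure.

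Section F.1 (Sample Size) uses the same 20 copies/mL boundary when it describes pilot participants whose "viral loads were either detectable (>20 copies/mL" or whose CD4 count was low. It sizes the trial on a proportion: "171 (85%) showed improvement (viral loads became undetectable or CD4 counts became >200 cell/mcL) at follow-up", against an assumed 45% under control. The result is 22 per group, raised to 25, with the aim of "attaining a power of at least 80% at the 0.05 level of significance for each of the comparisons". F.1 adds that power was also checked for outcomes analysed as means, but shows no mean, SD or scale.

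The documents contain no log transformation, no value for a result below 20, no rank or censored-data method, and no explicit below-20 analysis of viral load.

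**The concern.** The plan defines HIV control as a yes/no state, and its worked sample size uses a dichotomous outcome that includes undetectable viral load. The test it names for viral load compares means. In copies/mL a mean is a poor summary. A suppressed participant contributes almost nothing, viremic values can span several orders of magnitude, and the arm mean follows the one or two largest. As an illustration, a single participant at an assumed 100,000 copies/mL adds 100,000/25 = 4,000 copies/mL to the mean of an arm of 25.

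At stake is the HIV comparison. If one arm lost suppression in a meaningful share of participants, the named test would often miss it. Because Aim A anticipates no change, a non-significant result could easily be taken as support for that expectation.

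**Working it through.** **1. The plan's own figure.** Inputs from F.1: p1 = 0.85 (171/201 = 0.851), p2 = 0.45, power 80%, alpha 0.05 (taken as two-sided; the plan does not say). The pooled proportion is 0.65. With the usual two-proportion formula:

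n = [1.96·√(2 × 0.65 × 0.35) + 0.8416·√(0.85 × 0.15 + 0.45 × 0.55)]² / 0.40²
= [1.96 × 0.6745 + 0.8416 × 0.6124]² / 0.16
= (1.3220 + 0.5154)² / 0.16 = 21.1, so 22 per group.

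This matches the plan. By the same approximation, power at 25 per group is Φ[(0.40 × 5 − 1.3220)/0.6124] = Φ(1.107) = 86.6%; exact enumeration of the uncorrected chi-square gives 88.1%. The stated sample size therefore supports a comparison of proportions. It says nothing about a t-test on viral load.

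**2. Power of the named test.** The documents give no viral load distribution, so these are assumptions:
- suppressed results are set to 10 copies/mL;
- viremic values are log-normal with log10 mean 3 or 4 and SD 1;
- the F.1 rates are read as rates of suppression below 20.

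Simulated rejection rates at two-sided 0.05:

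| True rates below 20 | Per arm | t-test, copies/mL | t-test, log10 | chi-square, <20 or not |
|---|---|---|---|---|
| 85% vs 45% (plan) | 25 | about 12% | about 76-81% | about 88% |
| 85% vs 45% (plan) | 100 | about 33% | about 100% | about 100% |
| 85% vs 65% (illustrative) | 25 | about 4% | 30-34% | about 39% |
| 85% vs 65% (illustrative) | 100 | about 13% | 82-88% | about 91% |
| 85% vs 85% (no difference) | 25 | under 1% | 4-5% | about 5% |
| 85% vs 85% (no difference) | 100 | 1-2% | about 5% | about 5% |

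**3. Sensitivity to the assumed viremia.** With log10 mean/SD of 3.0/0.8, 3.5/1.0 and 4.5/0.8, and suppressed results set to 20, the copies/mL t-test at 85% vs 45% has 13-21% power at 25 per arm and 33-50% at 100 per arm. Chi-square has about 88% and about 100%. The log10 t-test has 77-84% at 25 per arm.

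**4. Cause of the loss.** In the step 3 settings at 85% vs 45% with 22 per arm, the single largest value carries a median 40-49% of all copies/mL in the trial, and the three largest carry 73-83%. Setting suppressed results to 0 instead of 20 changes the power of the copies/mL test by less than 1 point. The loss therefore comes from skew, not from the value given to results below 20. On the log10 scale that value does matter: the same change moves power by 1 to 7 points.

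**5. What the better test cannot do.** For 85% vs 65% with 25 per arm, the 95% confidence interval for the difference has half-width 1.96·√(0.1275/25 + 0.2275/25) = 1.96 × 0.119 = 0.23. With 100 per arm it is 0.12. At 25 per arm a 20-point difference is usually non-significant even with chi-square.

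**The case against.** The strongest reply is that E.2 does not state the scale. A statistician would probably take logs, and a log10 t-test with simple substitution recovers most of the power and holds its error rate (step 2). This stands as a limit on the claim: the copies/mL reading is inferred from silence, and the low power figures belong to that reading only. It does not remove the point, because the plan states neither the logs nor the value for results below 20 that logs would need.

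Second, a below-20 analysis is arguably already within the plan. Control is defined as a threshold, chi-square is assigned to categorical outcomes with blood pressure only as an example, and F.1 refers to both dichotomous and continuous forms. That is fair. But the only test the plan attaches to viral load by name is the t-test, so the two need reconciling.

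Third, the consequence is limited. Aim A only monitors HIV, the copies/mL test is conservative, and no text says that a non-significant result will be taken as proof of no change. All of this stands and lowers the severity.

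A reader might also infer that most results have no numeric value, so that no arm mean can be formed. The documents do not support this. They give no suppression rate for the enrolled population, no assay limit and no viral-load eligibility criterion. The 85% is a composite with CD4, from pilot participants who had detectable virus or low CD4 at baseline, and at the assumed 45% fewer than half of the control arm would be suppressed. As step 4 shows, missing numeric values are not what costs power in copies/mL.

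**Conclusion.** The point holds as a should-fix. The test named for viral load does not compare the control measure that E.2 defines, and its scale and below-limit handling are unspecified. In copies/mL, power at the plan's own 85% vs 45% with 25 per arm is about 12%, against about 88% for chi-square on below 20. At an illustrative 85% vs 65% with 100 per arm it is about 13% against about 91%. These figures rest on the assumed log-normal viremia and on reading the planning rates as suppression rates. The 65% is chosen for illustration and is not in the documents. The ordering held in every distribution tried.

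Two stronger readings should be resisted. One is that the named test would almost always miss a loss of control: at 85% vs 45% with 100 per arm it still rejects in about a third to a half of trials. The other is that the flaw threatens the trial's main conclusions: it produces missed differences rather than false positives, and it leaves the diabetes and hypertension analyses untouched.

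**What to change.** In E.2:

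- Replace the viral-load t-test with the proportion of participants with HIV-RNA below 20 copies/mL, compared by chi-square or Fisher's exact test. Name one in advance: at 85% vs 45% with 25 per arm, Fisher's test has about 80% power against 88% for the uncorrected chi-square.
- Report the difference in proportions with a 95% confidence interval, so that a non-significant result is not read as no change. At 25 per arm the interval matters more than the p-value.
- Records come from several providers (E.1), so reporting limits may differ. Classify a result reported only as below a higher limit by a fixed rule, with a sensitivity analysis the other way.
- Keep any continuous summary secondary, using a rank test or log10 values with a method for left-censored data.

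In F.1, reconcile the statement about power for means: say which outcomes it covers and on what scale, or remove viral load from it.

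The cost is wording in two sections and a dated change; no new data, visits or participants are needed. Recruitment ended by 31 October 2022 and visits end on 15 December 2023, so the change should be dated before viral loads are compared by arm. If any such comparison has already been made, say so. The one loss is that a binary outcome ignores the size of viremia, which the secondary analysis recovers.

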PI/SC are present to serve as scribes for the study pharmacist to aid in data acquisition accuracy and completeness. This is communicated in the consent form for telephonic MTM visits. PI/SC will be in compliance with all safety and confidentiality requirements as applicable.

Visit 3 - 9

All visits 3-9 will only take place via telephone or in-person per participant preference.

At the next MTM visit (arranged by the SC and agreed upon by both the participant and the study pharmacist), the study pharmacist will interview the participant to determine progress towards plan desired goals or targets. Upon completion of that interview, the study pharmacist will collaborate / discuss with participant and any or all medical providers as relevant or applicable to the plan and make changes to (update) the plan accordingly.

Once this is completed, the study pharmacist will discuss with the participant when the following MTM visit should take place. PI/SC will be present for each MTM visit they will serve as scribe (note taking on the paper CRF-Pharmacist updated from previous visit) for these follow-up visits and confirm accuracy of information recorded with study pharmacist as soon as possible following completion of the visit. CRF-Pharmacist will not be made available or visible to participant.

This sequence of events will be repeated approximately every 90 days (quarterly) for 2 years after enrollment. At the final visit, participants will be provided information on how to receive MTM visits outside of the study. As MTM is a service that is typically charged to a patient or their insurance company, the study is compensating Walgreens to provide MTM as part of the study. The amount of personal expense to a patient for MTM varies based on how the service is to be billed (cash vs. co-pay). This can also vary based on who provides the service (Walgreens vs. another pharmacy). The study pharmacist will explain anticipated personal cost to the participant at the final visit if MTM is continued at Walgreens only. This is communicated in the consent form in Visit 9. There is additional language in the Alternative to Participation section of the consent form.

UNTHSC team assessments:

A single, qualitative survey assessing barriers to care, health literacy, adherence and other domains will be administered verbally by the UNTHSC research team member at Visit 2-9. A single tool was decided upon after receiving feedback from key stakeholders.

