At each visit 2-9, consent to attain the records may be sought from the participant for any medical care received since the previous visit. This will be done for both groups. This process will follow that described in Screening Visit section. Participants will not be discontinued if records are not received. As a reminder as to why medical records are being sought for both groups, if this is not done for both groups, there is a risk that differences in health between the two groups could not be determined. This would not align with data safety monitoring plan.

If a participant withdraws consent to continue at any visit, permission to obtain medical records up until the date of withdrawal or discontinuation will be sought. This represents when information that would be used in the data would be received after discontinuation occurred as the information would have been recorded in the medical records prior to the discontinuation date.

Case report form compilation: CRF-Pharmacist will serve as the cumulative list of clinically meaningful (see further description in Screening Visit section) medical information extracted from the medical records (intervention group) as well as the findings of the study pharmacist performing the MTM (control group and intervention group).

CRF-Pharmacist and CRF-Staff are maintained electronically on the secure LabArchives platform. These are only accessible to UNTHSC research team personnel. Printed versions will be used during the MTM portion of each study visit. The study pharmacist will review and approve PI/SC hand notations made during the MTM portion of the visit. Once approved, PI/SC will update the forms electronically (using Word).

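### The plan collects baseline and interim A1c and blood pressure but names only one-value-per-person tests at the final visit, with no rule for missing final values

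*Combined protocol and SAP*

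**What the plan says.** On the endpoint, section F.1 (Sample Size) states: "The primary endpoint for this study will be the health indicators collected at the final follow-up visit comparing the corresponding intervention and control groups". Its example is intervention against control among men with diabetes.

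On the tests, section E.2 (Data Analysis and Data Monitoring) states: "Two sample t-test for continuous outcomes (viral loads) and chi-square for categorical outcomes (blood pressure under control or not) would be used". The level is 0.05. Viral load and blood pressure control are the examples given. A1c is an outcome through Specific Aim A, and no other test is named for it. The hypertension measure is a 10 mmHg systolic decrease or reaching goal.

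On repeated data, section E.1 (Screening visit) requests the previous 12 months of records at screening. Later requests run from every 90 days at most to every 12 months at least, and laboratory results and vital signs for all participants go into the database. Of the visits, E.1 (Visit 3 - 9) says: "This sequence of events will be repeated approximately every 90 days (quarterly) for 2 years after enrollment".

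On missing data, E.1 (UNTHSC team assessments) says: "Participants will not be discontinued if records are not received". No records are sought for dates after withdrawal. Section E.5 ends visits on 15 December 2023, and section F.5 reports enrollment complete as of 31 October 2022. There is no missing-data method, final-visit window or repeated-measures model. The only adjustment mentioned is in F.1: pharmacist access to a control participant's full record is to be controlled for.

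**The concern.** A t-test or chi-square on final values is unbiased only if, within each arm, having a final value is unrelated to disease control, or if any such relation distorts both arms equally. Here a final value exists only if a provider measured the indicator and the record reached the study.

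Loss could plausibly differ by arm. Participants learn their assignment before Visit 2. Those who demand the other arm are withdrawn. Only the intervention pharmacist receives record data and could see from it that a test is overdue.

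Two things are at stake. One is a bias that earlier values in the same database could reduce. The other is precision, since each planned comparison has about 25 people per arm. The planned tests leave this earlier information out, except that baseline blood pressure enters the 10 mmHg responder definition.

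**Working it through.** **1. The plan's own sample size.** Inputs from F.1: 171/201 = 85% ("Of these, 171 (85%) showed improvement") and 45% ("assuming a very conservative effect of 45% improvement for the control group"), alpha 0.05, power 80%. Two-sided testing is assumed.

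n = [1.96·√(2·0.65·0.35) + 0.842·√(0.85·0.15 + 0.45·0.55)]² / 0.40² = (1.322 + 0.515)² / 0.16 = 21.1, so 22 per group. This matches the plan, with power 81.7%.

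**2. Room for missing final values.** 22/25 = 0.88, so recruiting 25 allows for 12% without a final value. With 25 × (1 − m) analysed per arm:

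| Missing m | Analysed per arm | Power, 85% v 45% |
|---|---|---|
| 12% | 22 | 81.7% |
| 20% | 20 | 77.7% |
| 30% | 17.5 | 71.7% |
| 40% | 15 | 64.5% |

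The missing rates are assumptions. The 85% and 45% describe HIV improvement, not A1c or blood pressure, so the table shows only how loss erodes the stated power. F.1 expects dual-diagnosis participants to enlarge the groups, which would offset some of it.

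**3. Administrative stop.** Anyone enrolled after 15 December 2021 cannot reach 24 months by 15 December 2023. Someone enrolled on 31 October 2022, the latest date possible, has about 13.5 months. The documents do not say how many are affected.

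**4. Bias, illustrated.** Assumptions: no true effect; A1c SD 1.8; 85% of the intervention arm measured at the end; in the control arm 85% measured if the prior A1c is below the mean and 60% if above; correlation ρ between prior and final value 0.5-0.8.

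- Mean prior value among measured controls, in SD units: 0.798 × (0.60 − 0.85)/(0.60 + 0.85) = −0.138, where 0.798 = √(2/π).
- Shift in the control final mean: ρ × 1.8 × (−0.138) = −0.12 at ρ = 0.5 and −0.20 at ρ = 0.8. The intervention falsely looks worse by 0.12-0.20.
- Reverse the assumption, so that poorly controlled controls are measured more often, and the intervention falsely looks better by 0.12-0.20.
- Let only the rate differ (85% v 72.5%, unrelated to A1c) and the bias is 0.
- For scale, measured numbers are 25 × 0.85 = 21.25 and 25 × 0.725 = 18.1, so SE = 1.8·√(1/21.25 + 1/18.1) = 0.58. The bias is about 0.2-0.35 SE, and the type I error moves from 5% to about 5.5-6.4%.

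**5. What earlier values can repair.** In the step 4 scenarios, using the prior value brings the bias to about 0, because missingness was made to depend only on an observed quantity. If the same 85%/60% rates depend on the final value itself, the raw bias is 1.8 × 0.138 = 0.25, and 0.09-0.18 remains after adjustment for the prior value.

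**6. Precision at 30% missing.** The gain is the rise in effective sample size over 17.5 completers per arm, from generalised least squares with monotone dropout.

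- Interim values only, correlation 0.4-0.6: about 0.5-15%. Yearly records give 3-7% if correlation is constant over time and under 1% if it decays as AR(1). Quarterly records under AR(1) give 1-3%.
- Baseline included: about 1-67%. At constant correlation 0.5 with quarterly values, the model is worth 24.9 per arm, and 24.9/17.5 = 1.42, a 42% gain. Under AR(1) at 0.5 it is worth 17.8, about 2%.
- Where the gain is large, most of it comes from baseline: full adjustment at correlation 0.5 alone gives 1/(1 − 0.5²) = 1.33.

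**The case against.** The strongest reply is that complete-case deletion is nowhere written. This is correct: it is only what these tests do when no rule is given. The final follow-up visit could be read as the last available value. Records up to the withdrawal date are sought and late-arriving ones are used, so a withdrawn participant may still contribute. The promise to control for pharmacist access to records also implies some adjusted model, since a t-test or chi-square cannot do it. All this stands, but it shows that the analysis needs specifying.

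A reader might infer that the intervention, by prompting overdue tests, biases the comparison in a known direction. The documents do not support that. Prompting changes the measurement rate, which alone gives no bias, and nothing in the plan says whether poorly controlled control participants are tested less or more often. The administrative stop should also fall on both arms about equally under 1:1 randomization.

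A reader might also infer that a repeated-measures model would largely remove any bias. Step 5 shows that it need not.

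Nor should quarterly outcome data be assumed. The three-month A1c interval in E.2 describes monitoring practice, while the study commits only to yearly record requests. With sparse records and decaying correlation, the precision gain is close to nil.

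**Conclusion.** The point holds as a weakness of the stated analysis. The endpoint is at the final visit, the named tests use one value per person, and nothing says what happens when that value is absent, although the database holds baseline and interim values for both arms.

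Bias is possible but not shown. It requires missingness to depend on disease control differently by arm. The figure of 0.12-0.20 A1c points either way rests on the assumed SD, measurement rates and correlation, and is small beside the standard error at this sample size. The precision gain is equally dependent on assumptions: about 0.5-15% from interim values alone and about 1-67% with baseline, at 30% missing.

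The change is worth making because it is cheap, uses data already collected and rests on a weaker missing-data assumption. It is not evidence that the trial's result will be wrong.

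**What to change.** In section E.2, for A1c and systolic pressure:

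- Make the primary analysis a likelihood-based repeated-measures model on all dated record values, with baseline value, sex and comorbidity strata, arm, window and arm-by-window. A stratum factor that is constant within a comparison drops out of that fit.
- Use a few wide windows and a parsimonious covariance. About 50 people per comparison with irregular records will not support an unstructured matrix over eight quarters.
- Define the final window, including for participants cut short by the 15 December 2023 stop, and take the arm contrast there as primary.
- For the yes/no outcomes (A1c of 7% or less; 10 mmHg decrease or goal), multiply impute the underlying values by arm from the same variables, then classify.
- Keep the final-value t-test and chi-square as sensitivity analyses, and report the percentage with a final value by arm.
- Add a missing-not-at-random sensitivity analysis, because the model does not remove bias that depends on the unseen value.

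The cost is plan wording and some programming. The downside is reliance on a missing-at-random assumption, which the last item tests.
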